Statistical Analysis Plan

Title of Research: Aerodentis Clinical Trial: Assessment of the Efficacy of

Orthodontic Tooth Movement Using the Aerodentis System

UAB IRB Protocol #: F160418007

Principal Investigator: [name] [name], BDS, MScD, PhD.

Co-investigators: [name], DMD, PhD

[name], DDS

Sponsor: Dror Orthodesign Ltd.

[name]

[name]

[name]

Statistical Considerations

Overview and Rationale for Primary Parameter

The aims of this trial are to assess the safety and efficacy of the Aerodentis system in producing tooth movement. Safety is measured by absence of root resorption while efficacy is typically measured by various parameters relating to tooth movement. Because tooth movement is highly variable between individuals, treatment success is not usually contingent on a specific amount of movement over time. To this end we specify the primary endpoint, achieving score <1mm in Little's index

Design

Historical controls will be utilized as a comparator group. This historical data will be generated using the same inclusion/exclusion criteria as the proposed prospective single arm study. The historical patient population will be derived from the study sites participating in this prospective study. The study inclusion/exclusion criteria will be applied to consecutive patients treated with clear correctors that have the potential for complete datasets (as defined by the study protocol).

The use of single arm, open label trial with historical controls is supported when a device technology is well developed and the subject of interest is well understood^[1]. Orthodontic treatment of this patient population (i.e., use of mechanical force) is well developed and understood. In addition, the primary

Page 1 of 3

Version Date: 9/27/2016

^[1] Draft Guidance for Industry, Clinical Investigators, and Food and Drug Administration Staff Design Considerations for Pivotal Clinical Investigations for Medical Devices, published August 15, 2011.

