endpoints of success are Objective Performance Criteria (OPC) (use of impressions to objectively measure tooth movement and Little's index scoring and independent radiographic evaluation of tooth resorption). The effectiveness OPC in the treatment of this patient population is a summative Little's index score of <1.5mm. The safety OPC is to allow for no tooth root resorption. The use of this study design is supported both by proposed FDA Gudiance⁵ and recent FDA approvals of devices with a high risk profile^[2]

Safety Analysis Set

The safety analysis set will consist of all patients from whom dental plaster impressions were taken for the purpose of treatment with Aerodentis.

Full Analysis Set

Primary efficacy analysis will be assessed using the Full Analysis Set (FAS). The FAS will consist of patients from the intent to treat (ITT) cohort who started treatment and have at least one post-baseline assessment, and have no major protocol violation as determined by blind review.

Missing Data:

Missing data will be handled for imputation the primary endpoint data for FAS subjects. Subjects with no post-baseline assessment will be imputed as failures and will not be included in the FAS population. The MMRM model (Mixed-effect Model for Repeated Measures), which is based on MAR (missing at random) assumption will be applied to all the subjects of the FAS population. Sensitivity analyses will be applied for testing the effect of the imputation on the treatment effect. This will show the influence of the imputation on the study results.

Per Protocol Analysis Set

Efficacy analyses will also be done on the Per Protocol subset. Per Protocol subset include all FAS subjects who completed the study according to the protocol with no protocol deviations.

Missing Values: Only observed data will be used in the Per Protocol Analysis Set; i.e. missing data will not be imputed.

Endpoints

Safety

The safety endpoints are adverse events, whether or not treatment related. Included will be amount of root repsorption, measured by comparing x-rays before, mid-point and after treatment

Primary Efficacy

The primary endpoint will be to evaluate the degree of tooth movement. Treatment success will be defined using the Little's Index and when a score does not summative exceed 1.5mm (<1.5mm)

YGgDw&usg=AFQjCNGQWAFNwDj6XKq5ZVay8hssRm9lzA&bvm=bv.51156542,d.cWc

Page 2 of 3

Version Date: 9/27/2016

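### The SAP's failure rule for patients with no post-baseline assessment never reaches the primary analysis, and no efficacy analysis with a stated population restores them or the excluded major violators

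*SAP*

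**What the plan says.** The SAP (Full Analysis Set) assigns the primary efficacy analysis to the FAS. The FAS is made up of patients from the ITT cohort "who started treatment and have at least one post-baseline assessment, and have no major protocol violation as determined by blind review".

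The Missing Data section limits imputation of the primary endpoint to FAS subjects, and then says: "Subjects with no post-baseline assessment will be imputed as failures and will not be included in the FAS population". The repeated-measures mixed model, with its missing-at-random "assumption will be applied to all the subjects of the FAS population". The section adds: "Sensitivity analyses will be applied for testing the effect of the imputation on the treatment effect". It names no population or method for these sensitivity analyses.

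The only other efficacy set is nested in the first: "Per Protocol subset include all FAS subjects who completed the study according to the protocol with no protocol deviations". It uses observed data only. The closing paragraph of Statistical Analysis promises to assess the effects of noncompliance and dropout, again without a population or method.

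The SAP does not fully settle the form of the primary analysis. The reference to failures and the 1.5 mm success definition point to a proportion. The statement "The primary endpoint will be to evaluate the degree of tooth movement" also allows a continuous score.

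**The concern.** Counting patients who are never assessed as failures is a conservative choice, and a reader of the SAP would think it had been made. The second half of the same sentence cancels it. A programmer cannot tell which half is meant, and the choice could end up being made after scores are known.

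The exclusion of major violators raises a related problem. It belongs to a per-protocol analysis but sits in the primary set, and the term is undefined. Blind review helps, but the study is open label and the SAP does not say who is blinded to what. Protocol Section 18.a lists failure to wear the appliance as a risk to the desired result. If noncompliance were classed as a major violation, the primary set could lose patients whom the protocol expects to do worse.

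At stake are the denominator of the primary result and whether any planned analysis would show the effect of these exclusions.

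**Working it through.** **1. The plan's own figure.** The SAP (Sample Size Considerations) gives 40 subjects in the tested group; Protocol Section 15.a gives 30 active and 15 control. Neither document gives an expected success rate, power, margin or dropout allowance, so the 40 cannot be reproduced. The point does not depend on it.

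**2. Tracing the sets.**

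| Set or analysis | No post-baseline assessment | Major violators |
|---|---|---|
| FAS (primary) | out | out |
| Per Protocol (within FAS, observed data only) | out | out |
| ITT cohort | named only as the source of the FAS; undefined, no analysis assigned | same |
| Safety set | not assigned to efficacy | same |
| Sensitivity analyses; dropout assessment | population not stated | population not stated |

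The number of imputed failures in the primary denominator is therefore 0, however many patients lack an assessment.

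**3. Size, if success is a proportion.** Let n be all patients, k those removed, m = n − k, and s the successes. The gap between the FAS rate and the rate under the SAP's failure rule is

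s/m − s/n = (s/m) × (k/n).

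All values of s and k below are assumptions.

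| n | k | FAS rate | SAP's failure rule | Gap (points) |
|---|---|---|---|---|
| 40 | 1 | 31/39 = 79.5% | 31/40 = 77.5% | 2.0 |
| 40 | 2 | 30/38 = 78.9% | 30/40 = 75.0% | 3.9 |
| 40 | 4 | 29/36 = 80.6% | 29/40 = 72.5% | 8.1 |
| 30 | 1 | 23/29 = 79.3% | 23/30 = 76.7% | 2.6 |
| 30 | 2 | 22/28 = 78.6% | 22/30 = 73.3% | 5.2 |

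With visits every 4 weeks (Protocol Sections 13 and 16.a), one or two patients are the more plausible cases; four of 40 is an upper illustration. For k = 2 at n = 40, the exact (Clopper-Pearson) 95% interval moves from 62.7–90.4% to 58.8–87.3%.

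Varying the success rate with 2 of 40 removed: 19/38 = 50.0% gives a gap of 2.5 points, 23/38 = 60.5% gives 3.0, and 36/38 = 94.7% gives 4.7.

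**4. If the removed patients had in fact succeeded.** At n = 40 the FAS rate would be too low: 32/40 = 80.0% against 79.5% (0.5 points, k = 1), 80.0% against 78.9% (1.1, k = 2), and 33/40 = 82.5% against 80.6% (1.9, k = 4).

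**5. Violators.** Suppose 4 of 40 are removed and the FAS rate is 29/36 = 80.6%. Restoring them with v successes gives (29 + v)/40, which runs from 72.5% (v = 0) to 82.5% (v = 4). The direction is open.

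**6. FAS patients with no final score.** Suppose 2 of a FAS of 38 lack one and 29/36 = 80.6% is observed. The rate lies between 29/38 = 76.3% and 31/38 = 81.6%, depending on a rule that the SAP does not state.

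**The case against.** The strongest reply concerns size. Every count is assumed, and the plausible gap of 2.0 to 3.9 points is small beside an exact interval 27.7 points wide (90.4 − 62.7). The SAP sets no target success rate and the documents give no non-inferiority margin, so no conclusion can be shown to change. The 4-weekly visits, and the refunds to the Aerodentis group tied to compliance and completion (Protocol Section 16.h), may keep unassessed patients few. All of this stands and limits the severity.

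A second reply is that the failure rule may have been meant for an ITT sensitivity analysis. The preceding sentence, which confines imputation to FAS subjects, weakens that reading, but nothing rules it out. A reader might therefore infer that these patients are missing from every efficacy analysis. The documents do not support that: the sensitivity analyses and the dropout assessment have no stated population and could include them.

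A reader might also infer that the mixed model cannot yield a success status. That is too strong. Model-based predicted scores can be dichotomised; the SAP simply does not say how status would be derived. Nor does this defect require replacing the missing-at-random approach by counting every missing final score as a failure. In an assumed case with 6 of 36 final scores missing, that would move 24/30 = 80.0% to 24/36 = 66.7%, more than the gaps for one or two unassessed patients.

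**Conclusion.** The concern holds as an internal contradiction in the SAP, and it should be fixed. Followed literally, the text gives a primary result that the SAP's own failure rule cannot touch, on a set that also omits patients with an undefined violation. No efficacy analysis with a stated population would show either effect.

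The contradiction and the trace of the sets hold whether the primary analysis is a proportion or a continuous score. The figures assume a proportion and assumed counts: 2.0 points for one and 3.9 points for two unassessed patients of 40, or 2.6 and 5.2 of 30.

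It is tempting to conclude that the FAS rate is biased upward. The documents do not support this. The true outcomes of unassessed patients are unknown, and the FAS rate would be slightly too low had they succeeded. Removing violators can move the rate either way. What is shown is a departure from the SAP's own rule.

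**What to change.** - Define the ITT cohort. Delete the clause that keeps patients with no post-baseline assessment out of the FAS, and drop the post-baseline-assessment and major-violation conditions from the primary set.
- In that set, apply the SAP's failure rule to every ITT patient with no post-baseline assessment. This includes patients who never start treatment, so the started-treatment condition must go too. Also report non-starters separately by count and reason.
- Move the major-violation exclusion to the Per Protocol set, using a list fixed before scores are read. State who is blinded to what in the review.
- Keep the mixed model for patients with at least one post-baseline assessment. If the primary analysis is a proportion, state how success status is derived from it. Report failure imputation of other missing final scores only as a sensitivity analysis.

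**Cost.** SAP wording, some programming, and possibly a slightly lower reported success rate. The SAP (Design) selects historical controls for likely complete data, so imputed failures may fall mainly on the Aerodentis group. In the protocol's two-arm design, equal imputation would shrink a difference: an assumed 80% against 90%, with 10% imputed as failures in each arm, becomes 0.9 × 80 = 72% against 0.9 × 90 = 81%, or 9 points instead of 10, which favours non-inferiority. The number imputed in each group should therefore be reported beside the Per Protocol result.

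The conflict between the SAP Overview ("we specify the primary endpoint, achieving score <1mm") and the 1.5 mm threshold elsewhere, and the missing assessment time, are separate issues.

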### 13. Purpose—in nontechnical, lay language

Summarize the purpose and objectives of this protocol, including any related projects, in one short paragraph.

**The purpose of this study is to evaluate the efficacy of the Aerodentis system for orthodontic tooth movement in an open label, two-arms, non-inferiority clinical study. This open label, two-arm study will follow 45 patients for up to fifteen (15) months. Thirty participants will wear the Aerodentis device, and fifteen participants will wear Invisalign. Patients will be assigned to participate in the treatment group using the Aerodentis device at home for 10 hours daily or in the control group using**

clear correctors for the duration of up to 15 months. Outcome assessments will be performed every 4 weeks. Assessments will include tooth movement and quality of life assessments.

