**Exclusion:**

- 1. Any medical or dental condition that, in the opinion of the investigator, could negatively affect study results during the expected length of the study. Conditions can include poor oral hygiene, extensive dental treatments, or periodontal disease.**
- 2. Patient is currently using any investigational drug or any other investigational device.**
- 3. Patient plans to relocate or move during the treatment period.**
- 4. Allergic to acetaminophen (use of aspirin or non-steroidal anti-inflammatory drugs is excluded for patients while on the study).**
- 5. Use of bisphosphonates (osteoporosis drugs) during the study.**
- 6. Pregnant females. Orthodontic treatment is not advised in pregnant females. Hormonal changes may affect tooth movement, the unborn fetus can be affected during mandatory x-rays, and unexpected complication in pregnancy may arise that could negatively affect orthodontic treatment.**
- 7. Patients that, in the opinion of the investigator orthodontist, are unable to comply with safe and effective device use.**
- 8. Patients that are likely unwilling to be compliant with device use, as determined by the questionnaire for compliance.**

d. If participants will comprise more than one group or stratification, describe each group (e.g., treatment/intervention, placebo, controls, sham treatment) **and** provide the number of participants anticipated in each group.

**This is an open label, two-arm, non-inferiority study. Patients will be systematically assigned to a treatment group (wearing the Aerodentis device) or control group (wearing clear aligners).**

Participants from the control group come from both current patients treated on site and new patients coming into the orthodontics clinics, requesting treatment with clear aligners.

- e. Indicate which, if any, of the special populations listed below will be involved in the protocol. Include the Special Populations Review Form (SPRF) if indicated.
- Pregnant Women: Attach [SPRF—Pregnant Women, Fetuses, Neonates/Nonviable Neonates](#)
  - Fetuses: Attach [SPRF—Pregnant Women, Fetuses, Neonates/Nonviable Neonates](#)
  - Neonates/Nonviable Neonates: [SPRF—Pregnant Women, Fetuses, Neonates/Nonviable Neonates](#)
  - Prisoners: Attach [SPRF—Prisoners](#)
  - Minors (<18 years old): Attach [SPRF—Minors](#)
  - Employees or students at institution where research conducted
  - Persons who are temporarily decisionally impaired

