Review of photos for establishing pool of participants	24 hours	once	 Res  Routine
Consent	20 minutes	once	 Res  Routine
Fitting of appliance (Aerodentis or Invisalign)	1 hour	once	 Res  Routine
Quality of life questionnaire – Aerodentis	5 minutes	once every 4 weeks	 Res  Routine
Aerodentis device wear	10 hours	daily	 Res  Routine
Clear Correctors wear	24 hours everyday	daily	 Res  Routine

f. Will an interview script or questionnaire be used? Yes No  
**If Yes**, attach a copy.

g. Will participants incur any costs as a result of their participation? Yes No  
**If Yes**, describe the reason for and amount of each foreseeable cost.

Participants will be required to pay \$5000 for Aerodentis, or \$5000 for conventional clear aligners. Participants wearing the Aerodentis device will be ask to pay for treatment to assure compliance use with device. This is the same cost as all other UAB orthodontic patients incur for conventional clear aligner treatment, although, the participants wearing the Aerodentis device will be given compensation because the device is not familiar in the US and as a result the participants have uncertainty regarding its success and efficacy. Participants in the control group will be asked to pay regular price, without compensation, because Invisalign is a familiar treatment in the US and as a result the patient is certain regarding its process and results.

h. Will participants be compensated? Yes No  
**If Yes**, complete i-v:

- i. Type: (e.g., cash, check, gift card, merchandise): Check – Aerodentis group only
- ii. Amount or Value: One check for \$1000, three checks for \$550, one check for \$850
- iii. Method (e.g., mail, at visit): At visit
- iv. Timing of Payments: (e.g., every visit, each month): one check for \$1000 at participant recruitment, three refunds of \$550 each – depending on compliance of a minimum of 10 treatment hours a day, after every two months of treatment, and final refund of \$850 at treatment completion.

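### The primary efficacy set drops major protocol violators, the per-protocol set is nested inside it, and no all-treated efficacy analysis is planned, so both efficacy results condition on adherence

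*SAP*

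**What the plan says.** The SAP defines two efficacy sets.

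- **Full Analysis Set.** "Primary efficacy analysis will be assessed using the Full Analysis Set (FAS"). It consists of "patients from the intent to treat (ITT) cohort who started treatment and have at least one post-baseline assessment", who in addition "have no major protocol violation as determined by blind review".
- **Per Protocol Analysis Set.** "Per Protocol subset include all FAS subjects who completed the study according to the protocol with no protocol deviations". Efficacy is analysed on this set as well, using observed data only.

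Under Missing Data, one sentence says that patients with nothing recorded after baseline are scored as failures and also that they are outside the FAS. The rest of the FAS is handled with a mixed model for repeated measures. The only set free of any adherence or completion filter is the safety set, which includes everyone who had impressions taken for Aerodentis.

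Neither document defines a protocol violation or a deviation, or separates major from minor.

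The designs differ. Protocol section 15.d states: "This is an open label, two-arm, non-inferiority study", with 30 Aerodentis and 15 control patients (section 15.a). The SAP, under Design, states: "Historical controls will be utilized as a comparator group". It plans 40 subjects, all in the tested group, and a fixed success criterion of a Little's index below 1.5 mm. It gives no margin and no non-inferiority test.

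**The concern.** A primary set normally keeps patients whether or not they adhered, and a per-protocol set then shows what happens among those who did. Here the filter that usually defines a per-protocol set sits in the primary set, and the second set is stricter still. No planned efficacy analysis keeps the violators.

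This matters because adherence and outcome are linked in this trial. Protocol section 18.a lists, as a risk, that too little wear or incorrect use can prolong treatment and compromise the result. Patients removed for poor wear are therefore likely to include more than their share of failures. The reported success proportion would then describe adherent patients but be read as the result for treated patients.

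**Working it through.** **1. Who is in which set.** There is no stated set size to reproduce. The SAP's 40 cannot be re-derived either, since no power, expected rate, margin or dropout rate is given. The definitions can be set side by side:

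| Patient | FAS (primary) | Per-protocol | Any efficacy analysis |
|---|---|---|---|
| Started, assessed, completed, no deviation | yes | yes | yes |
| Started, assessed, minor deviation only | yes | no | yes |
| Started, assessed, major violation | no | no | none |
| Started, nothing after baseline | no | no | none, though scored as a failure |

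The last two rows are the problem. The failure score in the fourth row has no effect, because no efficacy analysis includes those patients.

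**2. Effect on the success proportion.** Let N patients start, S succeed, and k be excluded, v of them successes. The reported rate is (S − v)/(N − k) instead of S/N. It is higher whenever the excluded patients succeed less often than the rest, and unchanged if they succeed equally often.

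The documents give no success or violation rate, so these inputs are assumed: N = 30 (protocol, Aerodentis group), S = 20, and all excluded patients are failures (v = 0, the extreme case).

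| k excluded | Reported rate |
|---|---|
| 0 | 20/30 = 66.7% |
| 1 | 20/29 = 69.0% |
| 2 | 20/28 = 71.4% |
| 4 | 20/26 = 76.9% |

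Putting the four back one at a time (26, 27, 28, 29, 30 in the denominator) lowers the rate by 2.8, 2.6, 2.5 and 2.3 percentage points. With the SAP's N = 40 and the same two-thirds success rate, k = 4 gives 66.7% × 40/36 = 74.1%.

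**3. Size of the per-protocol set.** "Outcome assessments will be performed every 4 weeks" (protocol section 13), for at most 15 months. That is 15 × 30.44 = 457 days, and 457/28 gives 16 whole intervals. If each interval carries an independent chance p of any deviation, the expected number left is N × (1 − p)^16. The values of p are assumptions.

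| p per interval | Deviation-free share | of 30 | of 15 | of 40 |
|---|---|---|---|---|
| 1% | 85% | 25.5 | 12.8 | 34.1 |
| 2% | 72% | 21.7 | 10.9 | 29.0 |
| 5% | 44% | 13.2 | 6.6 | 17.6 |
| 10% | 19% | 5.6 | 2.8 | 7.4 |
| 20% | 3% | 0.8 | 0.4 | 1.1 |

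If treatment ended at 6 months (6 intervals), 28.2, 22.1 or 7.9 of 30 would remain at 1%, 5% or 20%. If a single day below 10 hours of wear counted, 30 × 0.999^457 = 19.0 would remain at 99.9% daily adherence and 30 × 0.99^457 = 0.3 at 99%. The answer depends almost wholly on what counts as a deviation and how often it happens.

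**The case against.** **A major violation may not mean poor wear.** The term is undefined and could be applied only to, say, eligibility errors. If so, the bias is smaller. But nothing in the SAP limits it that way, and the definition admits exclusions based on conduct after treatment starts.

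**The review is to be blind.** Blinding limits selection by someone who knows the results. It does not stop poor wear, judged without sight of the index, from being correlated with failure. The SAP also does not say what the reviewers are blind to in an open-label study.

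**Noncompliance and dropout are to be assessed.** The end of the SAP's Statistical Analysis section says so, but names no method and no analysis set, so it does not supply the missing analysis.

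**Two stronger readings are tempting and should not be drawn.**

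- A reader might infer that the per-protocol set will be nearly empty. The documents do not support this. No visit window or daily tolerance is given, and the refund term in protocol section 16.h ("depending on compliance of a minimum of 10 treatment hours a day") is a payment condition applied every two months, not a deviation rule. Fifteen months is a maximum. Deviations also tend to cluster within patients, which at the same average rate leaves more deviation-free patients than the independence formula gives.
- A reader might infer that no usable pair of analyses exists for non-inferiority. The SAP plans no non-inferiority test, so there is not yet a conclusion for a pair to support. The FAS as written could also serve as the adherent set. What is missing is the all-treated analysis.

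**Conclusion.** The point stands in this form: the primary efficacy set excludes major violators, the per-protocol set is a stricter subset of it, and no intent-to-treat or all-treated efficacy analysis is specified. The structure follows from the SAP's text alone. The direction of bias rests on one assumption, that at least some major violations concern wear or use, together with the protocol's own link between wear and result.

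The size is not known. In the assumed case, each excluded failure among about 30 patients moves the rate by roughly 2 to 3 percentage points, and four move it by about 10. In the single-arm design this acts directly on the success proportion. In the two-arm design each arm's proportion can be inflated, and the effect on the difference depends on how unevenly patients are excluded.

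The per-protocol set could hold anything from under 1 to about 25 of 30 patients under the per-interval rates tried. The supportable criticism is that its size cannot be predicted. Any statement about the two sets agreeing for non-inferiority must wait until the protocol (two arms, non-inferiority, 30 + 15) and the SAP (single arm, historical controls, 40) are reconciled.

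**What to change.** 1. In the Full Analysis Set definition, delete the condition "have no major protocol violation as determined by blind review" and the requirement for a post-baseline assessment, so that the primary analysis keeps all assigned patients who started treatment.
2. Under Missing Data, count patients with no post-baseline assessment as failures within that set. This removes the contradiction of scoring them as failures and leaving them out. Since the repeated-measures model has no post-baseline value for these patients, say that the failure score applies to the success proportion.
3. Define the per-protocol set as FAS patients who completed with no major protocol deviation. Fix the list of major deviations at the review already planned, before outcomes are examined, and state who is blinded at that review and to what.
4. If non-inferiority is intended, state the hypothesis and margin once protocol and SAP agree on the design.

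Items 1 to 3 take a few sentences and no extra data collection. The cost is that the primary result may be less favourable and that patients with minor deviations enter the per-protocol set.
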